Furthermore, Neymotin *et al.* (2011) examined 2 additional RTA 408 analogs, CDDO ethylamide (CDDO-EA) and CDDO-trifluoroethylamide (CDDO-TFEA), that potently activate Nrf2 in the G93A superoxide dismutase 1 (SOD1) mouse model of amyotrophic lateral sclerosis (ALS). CDDO-EA and CDDO-TFEA significantly induced the mRNA expression of the Nrf2 target genes NAD(P)H dehydrogenase, quinone 1 (NQO1), glutathione S-transferase A3 (GSTA3), and heme oxygenase-1 (HO-1) relative to controls while suppressing pro-inflammatory NF-κB target genes. Moreover, genes associated with increased mitochondrial biogenesis were also induced. Collectively, the data suggest that the ability of RTA 408 to activate Nrf2 and induce its target genes could potentially improve muscle function, oxidative phosphorylation, antioxidant capacity, and mitochondrial biogenesis in patients with mitochondrial myopathy.

Regarding the safety profile of RTA 408, no adverse effects were observed in the safety pharmacology studies. The genotoxicity potential of RTA 408 was investigated in 2 *in vitro* genetic toxicity tests and 2 *in vivo* genotoxicity studies in rats. The overall weight of evidence from the genotoxicity studies indicates that RTA 408 has a low genotoxicity risk to human subjects.

Version 5.0

The systemic toxicity potential of RTA 408 has been evaluated in multiple nonclinical Good Laboratory Practice (GLP) toxicity studies in rats, minipigs, and monkeys after oral and dermal (which produces meaningful systemic exposure to RTA 408 in animals) administration. The primary target organs for RTA 408 observed in the rat and monkey include the liver (increased liver weight, hepatocellular hypertrophy, bile duct hypertrophy and hyperplasia) and kidney (tubular degeneration/regeneration). These effects are considered to be mostly due to the known pharmacologic activity of RTA 408 in animals and likely do not reflect off-target toxicity. In rats (but not monkeys or minipigs), minimal to mild squamous cell hyperplasia of the forestomach and/or the limiting ridge of the stomach was observed and was fully reversible on treatment discontinuation. The forestomach and limiting ridge of the stomach do not exist in humans, a monogastric species. Therefore, this finding does not translate to humans and is not considered a relevant risk to humans.

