Overall, rats are more sensitive to the toxicologic effects of RTA 408 than minipigs or monkeys. In rats, the no-observed-adverse-effect level (NOAEL) following 28 days or 13 weeks or daily oral administration was 3 mg/kg/day, corresponding to an area under the plasma drug concentration-time curve (AUC)(0-24hr) of approximately 2.0 hr\*µg/mL. Following 6 months of oral administration to rats, adverse effects were observed at the lowest dose tested (0.3 mg/kg), which was associated with an AUC(0-24hr) of approximately 0.3 hr\*µg/mL. Similar systemic exposure was achieved in rats at the lowest dose tested in a 13-week topical dermal toxicity study of RTA 408 Lotion, with similar adverse effects observed in males, but not females, in the low-dose group. In monkeys, the NOAEL following 28 days or 13 weeks of daily oral administration was at least 100 mg/kg/day and the NOAEL following 9 months of daily oral administration was 30 mg/kg/day, corresponding to an AUC(0-24hr) of approximately 2.0 hr\*µg/mL. In a 13-week minipig dermal GLP toxicity study, the NOAEL was the maximal feasible dose of 8% RTA 408 Lotion (twice daily topical administration) with systemic exposures up to 1.7 hr\*µg/mL.

Across studies, the adverse liver findings in rats were reversible upon drug discontinuation and were associated with moderate to marked increases in serum gamma-glutamyl transpeptidase (GGT), alanine aminotransferase (ALT), aspartate aminotransferase (AST), and total bilirubin. With short treatment duration (i.e., 14 days), tubular degeneration/regeneration in rats was reversible with a 28-day treatment-free period in a non-GLP study. Although the kidney findings in rats after 28 days or longer of treatment were not reversible after a 4-week or 8-week recovery period, they were minimal to mild, were not associated with evidence of an effect on renal function (i.e., no increase in blood urea nitrogen [BUN] or serum creatinine), and were not present in minipigs or monkeys with dosing for up to 13 weeks (minipig dermal) or 9 months (monkey oral) at doses that produced systemic exposures approximately 10-fold above the exposures that elicited adverse kidney findings in rats.

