#### 14.2.4. Safety Variables

The safety variables include results of echocardiograms, ECGs, vital sign measurements, weight, BMI, physical examinations, AEs, SAEs, concomitant medications, and laboratory test results (clinical chemistry, hematology, urinalysis, microscopy, and pregnancy tests [as indicated]). All AEs will be coded using the Medical Dictionary for Regulatory Activities (MedDRA) and analyses of the AE data will be detailed in the SAP.

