# 2.4 Changes from Protocol-Specified Analysis

There are no planned changes to analyses from what is described in the protocol.

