## 7.2 Clinical Laboratory Evaluations

Clinical laboratory results (including chemistry, hematology, urine pH, and urine specific gravity) from the central laboratory and change from baseline will be summarized using descriptive statistics at each scheduled time point. Post-baseline laboratory assessments missing or below LLD will not be imputed, unless otherwise specified in Section 3. Box plot graphs and line graphs may be generated for selected laboratory tests, such as ALT, AST, GGT, creatine kinase (CK), and ferritin. Line graphs will include mean ± SE over time for both the observed values and for the change from baseline values.

In addition, a summary table will be provided for number and percentage of patients meeting the following pre-specified threshold level at any time during the study.

Table 5: Pre-Specified Threshold Levels for Categorical Laboratory Summaries

Lab Parameter	Pre-Specified Level
Magnesium	< 1.3 mEq/L (0.65 mmol/L)
BNP	> 200 pg/mL
ALT, AST	> 3 × upper limit of normal (ULN)
ALT, AST	> 8 × ULN
ALT, AST	> 5 × ULN for more than 2 weeks
ALT, AST, TBL	> 3 × ULN and (TBL > 2 × ULN × ULN)

Urinalysis results (other than pH and specific gravity) will not be summarized.

All laboratory results (including pregnancy test results) will be listed. Laboratory results that are above or below normal limits will be flagged in the listings.

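### SAP 7.2 leaves urine protein, blood and glucose out of the Part 1 laboratory summaries, although the kidney is a named target organ and urinalysis a declared safety endpoint

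*SAP*

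**What the plan says.** Protocol 5.1 lists two primary target organs in animals, the liver and the kidney. On the kidney it says that "the kidney findings in rats after 28 days or longer of treatment were not reversible after a 4-week or 8-week recovery period", that the findings were minimal to mild, and that they came with "no increase in blood urea nitrogen [BUN] or serum creatinine". It adds that they "were not present in minipigs or monkeys with dosing for up to 13 weeks" (minipig, dermal) or 9 months (monkey, oral), at exposures about 10-fold above those that produced adverse kidney findings in rats.

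Protocol 14.2.4 counts among the safety variables "laboratory test results (clinical chemistry, hematology, urinalysis, microscopy, and pregnancy tests [as indicated"]), and SAP 2.3.2 repeats this. Protocol 14.3 and SAP 3.1 both say that categorical data are summarised by frequencies and percentages.

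SAP 7.2 gives descriptive statistics for chemistry, hematology, urine pH and urine specific gravity. For the rest of the urine panel it says: "Urinalysis results (other than pH and specific gravity) will not be summarized". All laboratory results are listed, with values outside normal limits flagged. SAP Table 5 sets thresholds for counting patients by magnesium, BNP, transaminases and bilirubin. SAP 2.4 states: "There are no planned changes to analyses from what is described in the protocol".

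**The concern.** Safety and tolerability form a primary objective, and the kidney is one of only two organs that the protocol singles out from the animal work. In the rats that had the lesion, BUN and creatinine did not rise, yet those two markers, with creatinine-based eGFR, are most of what SAP 7.2 tabulates for the kidney. The trial also collects urine protein, blood and glucose, and the plan excludes exactly these from summary by an explicit sentence.

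At stake is whether a reader of the Part 1 laboratory tables could see a mild drift in urine findings across dose groups. With six active patients per cohort, such a drift would consist of a few patients in each group. It is easy to see in a table by dose and hard to see in individual listings.

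**Working it through.** The plan states no figure to reproduce. The check is to follow each kidney-related result to the outputs in which it appears.

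1. **Collected.** Protocol 9.9.15, Table 6, has eight dipstick items: specific gravity, ketones, pH, protein, blood, glucose, urobilinogen and bilirubin. Microscopy is done only if indicated. The schedule of assessments places urinalysis at eight visits: Screening, Day 1 and Weeks 1, 2, 4, 8, 12 and 16.
2. **Summarised.** SAP 7.2 keeps two dipstick items, pH and specific gravity, so 8 − 2 = 6 have no summary. SAP 7.2 does not name microscopy. Its exclusion follows because it belongs to the urinalysis panel and is in no list of summarised results.
3. **Threshold counts.** SAP Table 5 has 1 magnesium row, 1 BNP row, 3 ALT/AST rows and 1 combined ALT/AST and bilirubin row: 1 + 1 + 3 + 1 = 6. Four concern the liver and none the kidney.
4. **Serum markers.** SAP Appendix 1 places BUN, creatinine and eGFR in the chemistry panel, so they get descriptive statistics and change from baseline at each scheduled time point.
5. **Adverse event route.** Under protocol 12.6 a laboratory change becomes an adverse event only if it is judged clinically significant. SAP 7.1.1 then tabulates events by highest dose received.

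| Result | Summary by visit | Table 5 count | Flagged listing | Adverse event tables |
|---|---|---|---|---|
| BUN, creatinine, eGFR | yes | no | yes | if judged clinically significant |
| Urine pH, specific gravity | yes | no | yes | if judged clinically significant |
| Urine protein, blood, glucose | no | no | yes | if judged clinically significant |
| Microscopy, where done | no | no | yes | if judged clinically significant |

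The third row is the gap. A shift in protein, blood or glucose that investigators, judging one patient at a time under the blind, did not call clinically significant would reach no table by dose.

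6. **Consistency.** Protocol 14.3 and SAP 3.1 give a general rule for categorical data. SAP 7.2 makes an exception for results that SAP 2.3.2 names as safety endpoints, and SAP 2.4 says there are no changes. SAP 1 says that the SAP governs where it differs from the protocol, so the exception will be applied as written.

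**The case against.** The strongest objection concerns the biology. No statement in either document says that any urine marker moved in the rats with the lesion; protocol 5.1 gives only BUN and creatinine. That dipstick results would reveal tubular change is outside knowledge. This objection stands, and the point is not built on that claim. The protocol also calls the lesions minimal to mild, attributes the target-organ effects mostly to known pharmacology, and reports no kidney findings in minipigs or monkeys. This lowers the prior concern. It does not explain leaving a collected safety endpoint out of the tables.

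A second objection is that listing some results without summarising them is a legitimate choice. Protocol 14.2.4 names variables without promising a table for each, and protocol 14.3 makes the SAP the final arbiter. SAP 7.7 and 7.8 likewise rely on listings for non-significant physical findings and pregnancy results. The choice is indeed permitted. It is still an exception to the stated rule for categorical data, and SAP 2.4 does not disclose it.

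Third, Part 1 has six active patients per cohort and, by SAP 1.3, is not expected to characterise safety fully. That limits what any table can show, but counts by dose remain easier to read than listings.

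A reader might also infer more than the documents support:

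- **That a urinary signal would be invisible in all safety output.** It would be in flagged listings, and clinically significant changes reach the adverse event tables by dose.
- **That the kidney is not monitored.** BUN, creatinine and eGFR are summarised at each scheduled time point; what is missing is a threshold row.
- **That Part 2 dose selection would rest on these tables.** The DSMB recommends the cohort doses from unblinded analyses by an independent group, described in a separate document not available here. The SAP 7.2 tables are generally produced after the Part 1 lock. The SAP allows earlier analyses for planning Part 2 but does not tie them to these tables.
- **That the human treatment period carries the rat risk because it is longer than 28 days.** Comparing days across species without exposure shows nothing about risk.

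**Conclusion.** The point holds as a gap in presentation that should be closed. Six of eight dipstick items, including protein, blood and glucose, and any microscopy have no summary by dose in Part 1, and none of the six threshold rows is renal. A shift not judged clinically significant would be found only by reading listings. No error rate or estimate is affected.

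The conclusion rests on three things in the documents: the kidney is a named target organ, urinalysis is a collected and declared safety endpoint, and the categorical-data rule is set aside without disclosure. It does not assume that dipstick tests are sensitive to the rat lesion, and it uses only the rat text for the finding itself. It covers the Part 1 tables described in this SAP, and says nothing about the DSMB outputs or the separate Part 2 plan.

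**What to change.** Replace the sentence in SAP 7.2 with text to this effect: urine protein, blood and glucose will be summarised by dose group as category counts and as shifts from baseline at each scheduled visit, including Week 16, together with the worst post-baseline category; abnormal microscopy will be counted among patients examined. SAP 3.1 already provides for frequency tables, and SAP 3.7.4 already refers to worst post-baseline measures.

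Optionally, add two rows to Table 5, for reporting only and with no effect on patient management: creatinine >1.5 mg/dL and eGFR <60 mL/min/1.73 m². Both follow from the protocol's entry criteria, as the existing BNP row (>200 pg/mL) does. They would make the table consistent, but they do not answer the point that BUN and creatinine did not rise in the affected rats.

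If the sponsor prefers to keep these results in listings only, SAP 2.4 should say so and give the reason.

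The cost is a few more tables from data already collected. Some incidental abnormalities will need explaining, such as menstrual blood or glucose in patients with diabetes, who may enter with HbA1c up to 11.0%. Shifts from baseline limit the noise from findings present at entry.

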## 7.3 Vital Signs

Descriptive statistics for blood pressure, heart rate, respiratory rate, and temperature including baseline values and change from baseline values, will be summarized by time point. All vital signs parameters will be listed.

## 7.4 Body Weight

Descriptive statistics for body weight that are collected on the eCRF and change from baseline values will be will be summarized and listed by time point. Boxplot and line graphs of change from baseline over time for weight will be plotted.

## 7.5 Echocardiogram

Echocardiogram (ECHO) data, such as cardiac function [ejection fraction (%), left ventricular end-diastolic posterior wall thickness (PWTd), left ventricular end-diastolic septal thickness (LVSTd), left ventricular end-diastolic internal dimension (LVIDd), left ventricular end-systolic internal dimension (LVIDs), left atrial antero-posterior dimension, Right Ventricular Wall Thickness in diastole (RVWTd), left ventricle mass (index)] measurements are collected on the eCRF. Descriptive statistics for observed values and change from baseline will be presented for each ECHO assessment.

All ECHO parameters will be listed.

## 7.6 Electrocardiogram

Electrocardiogram (ECG) data, such as ventricular rate (bpm), PR interval (ms), QRS duration (ms), QT (ms), and QTc (ms) are collected on the eCRF. Descriptive statistics for observed values and change from baseline will be presented for each ECG assessment.

In addition, number and percentage of patients with any abnormal values (i.e., above a prespecified threshold) will be summarized by time point and overall while on study drug. The prespecified levels of ECG QTc thresholds are consistent with FDA guidance (See Table 6 below).

Table 6:	Pre-Specified	Threshold I	Levels for	ECG Parameters
----------	---------------	-------------	------------	----------------

ECG Parameter	Pre-Specified Level
PR	>200 msec
QTcF	>450, >480 or >500 msec, >30 or >60 msec increase from baseline
Heart rate	<40, >100 beats/min

All ECG parameters will be listed. Any results that exceed the above levels (provided in the above table) will be flagged in the listing.

# 7.7 Physical Examination

Abnormal clinically significant findings will be reported as Medical History or Adverse Events depending on day of onset. Abnormal non-clinically significant findings from physical examinations will be listed.

## 7.8 Pregnancy

A listing will be provided serum and urine pregnancy results of all on-study pregnancies, if applicable.

# 11. APPENDICES

Appendix 1. List of Laboratory Tests

Appendix 2. Programming Specifications

# Appendix 1. List of Laboratory Tests

Blood samples will be collected throughout the study for hematology, chemistry, and urinalysis for clinical laboratory evaluation.

Test panels will include the following:

Hematology	Chemistry	Urinalysis
Hematocrit	Blood urea nitrogen (BUN)	Specific gravity
Hemoglobin	Creatinine	Ketones
HbA1C	Total bilirubin	pH
Red blood cell (RBC) count	Alanine aminotransferase (ALT)	Protein
White blood cell (WBC)	Aspartate aminotransferase (AST)	Blood Glucose
Neutrophils	Alkaline phosphatase (ALP)	Urobilinogen
Bands (if detected)	Ferritin	Bilirubin
Lymphocytes	Sodium	Dilliuoni
Monocytes	Potassium	
Basophils (if detected)	Calcium	
Eosinophils (if detected)	Inorganic phosphorus	
Absolute platelet count	Magnesium	
Mean corpuscular	Chloride	
hemoglobin (MCH)	Bicarbonate	
Mean corpuscular volume	Uric acid	
(MCV)	Cholesterol	
Mean corpuscular hemoglobin concentration	Total protein	
(MCHC)	Glucose	
Reticulocyte count	Triglycerides	
	Albumin	
	Creatine phosphokinase (CPK)	
	Lactate dehydrogenase (LDH)	
	High-density lipoprotein cholesterol (HDL-C)	
	Low-density lipoprotein cholesterol (LDL-C)	
	Very-low-density lipoprotein cholesterol (VLDL-C)	
	Gamma-glutamyl transpeptidase (GGT)	
	Estimated glomerular filtration rate (eGFR) using the MDRD-4 formula	

## Appendix 2. Programming Specifications

Continuous data will be listed corresponding to the precision measured or calculated. Measures of central tendency will be presented using one additional decimal place than the precision of the data. Variability summaries will be presented using two additional significant digits relative to the precision of the underlying data. Quartiles, the minimum, and the maximum will be presented using the precision of the data. Rounding for derived values should be one additional decimal place to which the raw data were entered. For instance, if the raw data are rounded to the 0.001 decimal place, the derived values must be rounded to the 0.0001 decimal place.

All percentages are to be expressed as integers with one decimal place. The convention for rounding percentages is as follows:

- Values greater than or equal to x.x5% are rounded up
- Values between 0 and x.x5% are rounded down
